6.5 Permitted Concomitant Medications and Procedures

The following medications and procedures are permitted during the study:

- Antiemetics, including 5-HT₃ serotonin receptor antagonists, may be used at the discretion of the investigator.
- Loperamide or other antidiarrheal should be used for symptomatic diarrhea at discretion of the investigator. The dose and regimen will be according to institutional guidelines. IVF should be given to prevent volume depletion.
- Growth factors (eg, granulocyte colony stimulating factor [G-CSF], granulocyte macrophage-colony stimulating factor [GM-CSF], recombinant erythropoietin) are permitted. Their use should follow published guidelines and/or institutional practice. Erythropoietin will be allowed in this study. Their use should follow published guidelines and/or institutional practice.
- Patients should be transfused with red cells and platelets as clinically indicated and according to institutional guidelines.
- Patients who experience worsening neuropathy from baseline may be observed for recovery, and have dose reductions/delays as indicated in the protocol, and any supportive therapy or intervention may be initiated as appropriate at the discretion of the investigator.
- Supportive measures consistent with optimal patient care may be given throughout the study.

6.6 Precautions and Restrictions

- Fluid deficit should be corrected before initiation of treatment and during treatment.

- Nonsteroidal anti-inflammatory drugs (NSAIDs) should be avoided with impaired renal function given reported NSAID-induced renal failure in patients with decreased renal function.

Pregnancy

Thalidomide has caused severe birth defects when taken during pregnancy. Thalidomide should never be used by women who are pregnant or who could become pregnant whilst taking the medicine or could become pregnant within 4 weeks after stopping the medicine. Even a single dose can cause birth defects.(20) It is not known what effects ixazomib has on human pregnancy or development of the embryo or fetus.

Therefore, female patients participating in this study should avoid becoming pregnant, and male patients should avoid impregnating a female partner. Nonsterilized female patients of reproductive age group and male patients should use effective methods of contraception through defined periods during and after study treatment as specified below.

Female patients must meet 1 of the following:

- Postmenopausal for at least 1 year before the screening visit, or
- Surgically sterile, or
- If they are of childbearing potential, agree to practice 2 effective methods of contraception from the time of signing of the informed consent form through 90 days after the last dose of study drug, or
- Agree to practice true abstinence, when this is in line with the preferred and usual lifestyle of the subject. (Periodic abstinence [eg, calendar, ovulation, symptothermal, postovulation methods] and withdrawal are not acceptable methods of contraception.)

Male patients, even if surgically sterilized (ie, status postvasectomy) must agree to 1 of the following:

- Practice effective barrier contraception during the entire study treatment period and through 90 days after the last dose of study drug, or
- Agree to practice true abstinence, when this is in line with the preferred and usual lifestyle of the subject. (Periodic abstinence [eg, calendar, ovulation, symptothermal, postovulation methods for the female partner] and withdrawal are not acceptable methods of contraception.)

6.7 Management of Clinical Events

Adverse drug reactions such as thrombocytopenia, diarrhea, fatigue, nausea, vomiting, and rash have been associated with ixazomib treatment. Management guidelines regarding these events are outlined below. Further details of management of ixazomib AEs are described in Section 6 of the ixazomib IB.

Prophylaxis Against Risk of Reactivation of Herpes Infection

Patients may be at an increased risk of infection including reactivation of herpes zoster and herpes simplex viruses. Antiviral prophylaxis such as acyclovir, valacyclovir, or other antivirals should be initiated in all patients (Section 6.2.5).

Nausea and/or Vomiting

Standard anti-emetics including 5-hydroxytryptamine 3 serotonin receptor antagonists are recommended for emesis if it occurs once treatment is initiated; prophylactic anti-emetics may also be considered at the physician's discretion. Dexamethasone should not be administered as an anti-emetic. Fluid deficit should be corrected before initiation of study drug and during treatment.

Diarrhea

Prophylactic anti-diarrheals will not be used in this protocol. However, diarrhea should be managed according to clinical practice, including the administration of antidiarrheals once infectious causes are excluded. Fluid intake should be maintained to avoid dehydration. Fluid deficit should be corrected before initiation of treatment and during treatment.

Erythematous Rash With or Without Pruritus

As with bortezomib, rash with or without pruritus has been reported with ixazomib, primarily at the higher doses tested and when given with agents where rash is an overlapping toxicity. The rash may range from limited erythematous areas, macular and/or small papular bumps that may or may not be pruritic over a few areas of the body, to a more generalized eruption that is predominately on the trunk or extremities. Rash has been most commonly characterized as maculopapular or macular. To date, when it does occur, rash is most commonly reported within the first 3 cycles of therapy. The rash is often transient, self-limiting, and is typically Grade 1 to 2 in severity.

Symptomatic measures such as antihistamines or corticosteroids (oral or topical) have been successfully used to manage rash and have been used prophylactically in subsequent cycles. The use of a topical, IV, or oral steroid (eg, prednisone \leq 10 mg per day or equivalent) is permitted. Management of a Grade 3 rash may require intravenous antihistamines or corticosteroids. Administration of

ixazomib (and/or other causative agent if given in combination) should be modified per protocol and re-initiated at a reduced level from where rash was noted (also, per protocol).

In line with clinical practice, dermatology consult and biopsy of Grade 3 or higher rash or any SAE involving rash is recommended. Prophylactic measures should also be considered if a patient has previously developed a rash (eg, using a thick, alcohol-free emollient cream on dry areas of the body or oral or topical antihistamines). A rare risk is Stevens-Johnson Syndrome, a severe and potentially life-threatening rash with skin peeling and mouth sores, which should be managed symptomatically according to standard medical practice. Punch biopsies for histopathological analysis are encouraged at the discretion of the investigator.

Thrombocytopenia

Blood counts should be monitored regularly as outlined in the protocol with additional testing obtained according to standard clinical practice. Thrombocytopenia may be severe but has been manageable with platelet transfusions according to standard clinical practice. Ixazomib administration should be modified as noted as per dose modification recommendations in the protocol when thrombocytopenia occurs (see Table 6-2). Therapy can be reinitiated at a reduced level upon recovery of platelet counts. A rare risk is thrombotic thrombocytopenic purpura (TTP), a rare blood disorder where blood clots form in small blood vessels throughout the body characterized by thrombocytopenia, petechiae, fever, or possibly more serious signs and symptoms. TTP should be managed symptomatically according to standard medical practice.

Neutropenia

Blood counts should be monitored regularly as outlined in the protocol with additional testing obtained according to standard clinical practice. Neutropenia may be severe but has been manageable. Growth factor support is not required but may be considered according to standard clinical practice. Ixazomib administration should be modified as noted as per dose modification recommendations in the protocol when neutropenia occurs (see Table 6-2). Therapy can be reinitiated at a reduced level upon recovery of ANC.

Fluid Deficit

Dehydration should be avoided since ixazomib may cause vomiting, diarrhea, and dehydration. Acute renal failure has been reported in patients treated with ixazomib, commonly in the setting of the previously noted gastrointestinal toxicities and dehydration.

Fluid deficit should be corrected before initiation of study drug and as needed during treatment to avoid dehydration.

Hypotension

Symptomatic hypotension and orthostatic hypotension with or without syncope have been reported with ixazomib. Blood pressure should be closely monitored while the patient is on study treatment and fluid deficit should be corrected as needed, especially in the setting of concomitant symptoms such as nausea, vomiting, diarrhea, or anorexia. Patients taking medications and/or diuretics to manage their blood pressure (for either hypo- or hypertension) should be managed according to standard clinical practice, including considerations for dose adjustments of their concomitant medications during the course of the trial. Fluid deficit should be corrected before initiation of study drug and as needed during treatment to avoid dehydration.

Posterior Reversible Encephalopathy Syndrome

One case of posterior reversible encephalopathy syndrome, which ultimately resolved, has been reported with ixazomib. This condition is characterized by headache, seizures and visual loss, as well as abrupt increase in blood pressure. Diagnosis may be confirmed by magnetic resonance imaging (MRI). If the syndrome is diagnosed or suspected, symptom-directed treatment should be maintained until the condition is reversed by control of hypertension or other instigating factors.

Transverse Myelitis

Transverse myelitis has also been reported with ixazomib. It is not known if ixazomib causes transverse myelitis; however, because it happened to a patient receiving ixazomib, the possibility that ixazomib may have contributed to transverse myelitis cannot be excluded.

6.8 Preparation, Reconstitution, and Dispensing

Ixazomib and thalidomide are anticancer drugs and as with other potentially toxic compounds caution should be exercised when handling ixazomib or thalidomide capsules/tablets.

6.9 Packaging and Labeling

The study drug ixazomib capsules will be provided by Millennium. The study drug will be labeled and handled as open-label material, and packaging labels will fulfill all requirements specified by governing regulations.

The capsules are individually packaged using cold-form foil-foil blisters that are in a child-resistant carton. There are 3 capsules in each wallet/carton.

Thalidomide and dexamethasone will be commercially obtained and all packaging and labeling procedures should be adhered to.

6.10 Storage, Handling, and Accountability

Upon receipt at the investigative site, ixazomib should remain in the blister and carton provided until use or until drug is dispensed. The container should be stored at the investigative site refrigerated (36°F to 46°F, 2°C to 8°C). Ensure that the drug is used before the retest expiry date provided by Millennium. Expiry extensions will be communicated accordingly with updated documentation to support the extended shelf life.

Ixazomib capsules dispensed to the patient for take-home dosing should remain in the blister packaging and refrigerated as noted above until the point of use. The investigative site is responsible for providing the medication to the patient in the correct daily dose configurations. Comprehensive instructions should be provided to the patient in order to ensure compliance with dosing procedures. Patients who are receiving take-home medication should be given only 1 cycle of medication at a time. Patients should be instructed to store the medication refrigerated (36°F to 46°F, 2°C to 8°C) for the duration of each cycle. Patients should be instructed to return their empty blister packs to the investigative site, rather than discarding them. Reconciliation will occur accordingly when the patient returns for their next cycle of take-home medication. Any extreme in temperature should be reported as an excursion and should be dealt with on a case-by-case basis.

Because ixazomib is an investigational agent, it should be handled with due care. Patients should be instructed not to chew, break, or open capsules. In case of contact with broken capsules, raising dust should be avoided during the clean-up operation. The product may be harmful by inhalation, ingestion, or skin absorption. Gloves and protective clothing should be worn during cleanup and return of broken capsules and powder to minimize skin contact.

The area should be ventilated and the site washed with soap and water after material pick-up is complete. The material should be disposed of as hazardous medical waste in compliance with federal, state, and local regulations.

In case of contact with the powder (eg, from a broken capsule), skin should be washed immediately with soap and copious amounts of water for at least 15 minutes. In case of contact with the eyes, copious amounts of water should be used to flush the eyes for at least 15 minutes. Medical personnel should be notified. Patients are to be instructed on proper storage, accountability, and administration of ixazomib, including that ixazomib is to be taken as intact capsules.

Thalidomide and dexamethasone will be supplied by the site via the pharmaceutical benefits scheme (PBS) from commercial sources and must be stored according to the instructions provided in the manufacturer's package insert.

6.11 Study Compliance

Study drug will be administered or dispensed only to eligible patients under the supervision of the investigator or identified sub-investigator(s). The appropriate study personnel will maintain records of study drug receipt and dispensing.

6.12 Termination of Treatment and/or Study Participation

Patients will be informed that they have the right to withdraw from the study at any time for any reason, without prejudice to their medical care. The investigator also has the right to withdraw patients from the study for any of the following reasons:

- Adverse event
- Protocol violation
- Suspected pregnancy
- Lost to follow-up
- Progressive disease
- Study terminated
- Other

Patients who are withdrawn from the study will not be replaced.

At the time of withdrawal, all study procedures outlined for the End of Study visit should be completed. The primary reason for patient's withdrawal from the study should be recorded in the source documents and CRF.

7. STATISTICAL AND QUANTITATIVE ANALYSES

7.1 Statistical Methods

The primary efficacy and safety analyses will be conducted after all patients, who are still receiving ITD combination therapy have completed 4 cycles of therapy. The additional data for patients continuing to

receive study treatment beyond this time, as allowed by the protocol, will be summarized in a final report once all patients remaining on study have completed 1 year of follow-up.

The primary efficacy analysis will be an intention-to-treat analysis conducted on the Full Analysis Set (FAS) which comprises all patients registered on the study. A sensitivity analysis of the primary efficacy endpoint will also be conducted on the Per-Protocol Set (PPS) which consists of a subset of patients in the FAS who have been compliant with the requirements of the protocol, i.e. patients without a major protocol deviation. Major protocol deviations include, but are not limited to, incomplete documentation of response status at registration, a response status of MR or better at registration, and, other anti-neoplastic therapy administered after registration on the study. Major protocol deviations will be documented, and the PPS will be determined, prior to locking the database for the primary efficacy analysis. The primary safety analysis will be conducted on the Safety Set which consists of the subset of patients in the FAS who received at least one dose of ixazomib.

Demographic and other baseline data collected at registration will be summarized descriptively for the FAS. Categorical data will be presented as frequencies and percentages. For continuous data, means, standard deviations, medians, 25th and 75th percentiles, minima and maxima will be presented.

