4.3 Duration of Study

It is estimated that recruitment will take 12 months.

- Based on previous experience in the MM14 trial (a prospective randomised phase 2 study of single agent pomalidomide maintenance versus combination pomalidomide and low dose dexamethasone maintenance following induction with the combination of pomalidomide and low dose dexamethasone in patients with relapsed and refractory

myeloma previously treated with lenalidomide) where 13 patients were recruited in a similar population within 6 months in a single centre it is reasonable to consider that recruitment of 45 patients at multiple sites within 12 months is feasible.

Number of months from Takeda approval to site activation of study: 3

Number of months from study activation to first patient in (FPI): 3

Number of months from last patient in (LPI) to last patient out (LPO): 24

Number of months from LPO to Final data/Manuscript: 6

It is estimated that the average number of cycles per patient will be 4. Patients will continue on protocol treatment (combination therapy) until any of the following occurs:

- Unacceptable toxicity/adverse event that may cause severe or permanent harm which rule out continuation of the study drug
- Relapse/progressive disease (as defined by IMWG – Appendix 3)
- Consent withdrawal
- Major violation of the study protocol
- Suspected pregnancy
- Death

Following cessation of ITD therapy patients will remain on trial for a follow up phase to document progression free survival, salvage therapy, response to salvage therapy and survival following salvage therapy (PFS2, second PFS), date of death. Follow up will continue until all patients remaining on study have been followed for at least 12 months.

The trial may also be terminated early by the TMC if safety concerns emerge with this treatment.

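### The Per-Protocol Set excludes patients given any other anti-neoplastic therapy after registration, with no end point, so expected salvage therapy counts as a major deviation and can bias the sensitivity ORR upward

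*Protocol*

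**What the plan says.** Section 7.1 runs the primary efficacy analysis on the FAS (all registered patients) and adds one sensitivity analysis of the same endpoint on the PPS. The PPS is made up of "patients in the FAS who have been compliant with the requirements of the protocol, i.e. patients without a major protocol deviation". Three examples of major deviation are named, and the list is described as not exhaustive. The third is "other anti-neoplastic therapy administered after registration on the study". It has a start (registration) but no end. On timing, deviations are documented and "the PPS will be determined, prior to locking the database for the primary efficacy analysis"; that analysis takes place once all patients still on ITD have completed 4 cycles.

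Section 4.3 describes what follows treatment: "Following cessation of ITD therapy patients will remain on trial for a follow up phase to document progression free survival, salvage therapy", together with response to salvage and survival after it. The progression-data footnote to the Schedule of Events lists the same items. Section 4.3 also expects recruitment to take 12 months and says: "It is estimated that the average number of cycles per patient will be 4".

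**The concern.** The protocol plans to collect data on an event that its own deviation list treats as major non-compliance. Salvage therapy normally follows failure of the study regimen, so an exclusion triggered by salvage depends on the outcome being measured. A patient whose disease progresses on ITD without a response is likely to receive other therapy and leave the PPS, while a patient with a lasting response stays in.

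What is at stake is the use of the PPS as a robustness check. If it is shaped by how patients fared on ITD, its agreement or disagreement with the FAS says little about protocol compliance and may only reflect which failures were removed. The exclusion is also not needed to keep the endpoint clean. Section 3.1 counts response only while on ITD, and Appendix 11.4 requires the confirming assessments to come before any new therapy. Salvage given later cannot create a response that counts.

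**Working it through.** **The plan's own rule, reproduced.** Inputs from sections 7.1.1 and 7.1.6 are n = 45, prior Beta(0.86805, 1), observed ORR of at least 60%, and a 90% posterior probability that the true ORR exceeds 45%. The smallest number of responders meeting both criteria is 27 of 45 (posterior probability 0.977). At a true ORR of 65%, the probability of 27 or more is 0.806, against the stated 0.80. At a true ORR of 45% it is 0.031. The FAS rule therefore behaves as described.

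**Whether salvage can occur before the PPS is fixed.** Four 28-day cycles are 112 days, about 3.7 months. Assume even accrual over 12 months, and that the last patient stays on ITD for 4 cycles. Mean time since registration at the primary analysis is then about 6 + 3.7 = 9.7 months, against an expected average of about 3.7 months on treatment. Patients who failed early could have started other therapy by then. The protocol does not say how many.

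**Expected PPS ORR.** Let p be the true ORR, f the share of non-responders salvaged before the PPS is fixed, and g the same share of responders. Then

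PPS ORR = p(1 − g) / [p(1 − g) + (1 − p)(1 − f)].

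This exceeds p exactly when f > g and equals p when f = g. The values of f and g below are assumptions. With p = 0.45 and f = 0.50, the non-responder term is 0.55 × 0.50 = 0.275:

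| g | Calculation | Expected PPS ORR |
|---|---|---|
| 0% | 0.450 / (0.450 + 0.275) | 62.1% |
| 10% | 0.405 / (0.405 + 0.275) | 59.6% |
| 25% | 0.3375 / (0.3375 + 0.275) | 55.1% |
| 50% | 0.225 / (0.225 + 0.275) | 45.0% |

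Holding g at 0, f = 25% gives 0.45 / (0.45 + 0.4125) = 52.2%, and f = 75% gives 0.45 / (0.45 + 0.1375) = 76.6%. These are one-sided cases, because no responder is lost.

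**In patient counts.**
- An FAS result of 25/45 (55.6%) becomes 25/41 (61.0%) if 4 salvaged non-responders are removed.
- 23/45 (51.1%) becomes 23/38 (60.5%) if 7 are removed.
- 20/45 (44.4%) becomes 20/33 (60.6%) if 12 are removed. If 2 salvaged responders go as well, it is 18/31 (58.1%); if 5 go, 15/28 (53.6%).

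**With the deviation limited to the treatment period.** Salvage after ITD removes nobody, and at a true ORR of 45% the expected PPS ORR stays at 45%.

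**The case against.** The best defence is that the phrase was meant for therapy given alongside ITD. It is offered as an example of non-compliance, and salvage that the protocol itself provides for is hardly non-compliant. Section 6.4 bars other anti-myeloma treatment under a heading about concomitant medication. Section 4.3 lists a major protocol violation as a reason to stop ITD, which suggests that violations were thought of as arising on treatment. That intent is plausible, but the text does not state it. Section 6.4 applies its bar during the study, and section 4.3 keeps patients on trial after ITD, so neither supplies the missing limit. A non-exhaustive list lets later documents add deviations; it does not withdraw one already named. The SAP was not available and may clarify the rule, but the protocol wording would still need to agree with it.

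Several stronger readings are tempting and are not supported:
- *The rule removes failures and keeps responders.* A responder who relapses and receives salvage before the PPS is fixed is excluded too. This offsets the bias and cancels it when the two shares are equal. Non-responders with minimal response or stable disease may also remain on ITD, and others may die or withdraw without salvage, so high values of f should not be presumed.
- *A regimen at the futility rate could be declared effective.* Section 7.1.6 divides by all registered patients and attaches both proof-of-concept criteria to that analysis. A PPS figure above 60% triggers no declaration.
- *The lock comes at least 4 cycles after the last patient starts.* The 4-cycle condition covers only patients still receiving ITD, so the lock could come sooner.
- *There is no other sensitivity analysis.* One can say only that this protocol names no other.

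**Conclusion.** The concern holds as a defect in how the PPS is defined. Followed as written, section 7.1 excludes patients for receiving therapy that section 4.3 expects and records. The resulting PPS ORR is biased upward if non-responders are salvaged more often than responders before the set is fixed. That is the likely direction for a primary analysis tied to 4 cycles, but it is an expectation and not a figure in the protocol. Under the assumed shares at a true ORR of 45% with half of non-responders salvaged, the distortion runs from 17 percentage points (no responders salvaged) to none (half of responders salvaged). The FAS analysis, the sample size and the proof-of-concept decision stand. The point deserves correction because it concerns the one named sensitivity analysis of the primary efficacy endpoint and is simple to put right.

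**What to change.** In section 7.1, replace the third example of a major deviation with: *other anti-myeloma therapy administered after registration and before the earlier of documented progression or permanent discontinuation of all study treatment*. Add a sentence stating that salvage therapy after that point is not a deviation for the PPS, and carry the same definition into the SAP. Referring to all study treatment matters because section 6.3 lets patients stay on study with the remaining agents after one is stopped.

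The cost is one phrase and one sentence. The change affects only the definition of an analysis set and needs no new data, since salvage therapy is already recorded. The only downside is a possibly less favourable PPS figure.
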